- a) Calculate the rate of recruitment, defined as the number of participants enrolled in the study out of the number of MMT patients who are potentially eligible and approached for participation. The average monthly rate of participants starting pharmacy-based methadone dispensing for OUD among enrolled participants will also be calculated. The number of potential participants pre-screened and the reasons for pre-screen failure and screen failure will also be evaluated.
- b) Calculate the adherence to methadone treatment defined as (1) the proportion of methadone take-home doses dispensed at the pharmacy out of the total number of take home doses prescribed and (2) the proportion of successful scheduled methadone dose call-back with no signs of methadone diversion.
- c) Examine retention in treatment, as determined by the proportion of participants who remain in treatment at the pharmacy during the 3-month follow-up phase.

- d) Examine the proportion of positive urine drug screens (UDS) over the study duration.
- e) Examine the number of days of self-reported substance use (alcohol intoxication, and other drugs) as collected on Timeline Followback (TLFB) over the study duration (Sobell, 1992; Sobell & Sobell, 2000).
- f) Determine indicators of participant satisfaction with treatment delivery measured using the Treatment Satisfaction Survey (adapted from Harland et al., 2005) obtained at each assessment; proportion of visits in which raters are satisfied (score of 4 on a Likert Scale of 1-5) or very satisfied (score of 5 on a Likert Scale of 1-5).
- g) Determine pharmacist and physician satisfaction with treatment delivery measured using the Treatment Satisfaction Survey at follow-up assessment, and a proportion of physician and pharmacist ratings of satisfied or very satisfied.
- h) Examine participant safety, as measured by: (1) Any fatal or non-fatal substance-related overdose measured by medical examiner record or self-report, respectively; and (2) Any substance-related emergency department (ED) visit or hospitalization, measured by self-report.

3. Background and rationale

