4.4. Assessments

Study assessments will focus on the feasibility (e.g., recruitment, implementation of the intervention), treatment adherences, and safety measures. A list of assessments by the study visit is summarized in **Table 1**. Assessments are categorized as either general and medical assessments, safety assessments, substance use assessments, or methadone treatment and satisfaction assessments. A detailed description of each assessment is provided following the study assessment timetable.

Table 1: Study Assessment Timetable

Study visit number	Visit 1	Visit 2*_	Visit 3	Visit 4	Visit 5	Early termination	
Visit location**	OTP/remote	Pharmacy	OTP, Pharmacy, remote	OTP, Pharmacy, remote	OTP, Pharmacy, remote	OTP, Pharmacy, remote	
Assessment/Activity	Screening/ Baseline	Methadone dosing and dispensing	1 Month After Visit 2	2 Months After Visit 2	3 Months After Visit 2		As needed
General and Medical Assessments							
Recruitment Log	x						
Prisoner Status Assessment	x		x	x	x		x
Informed Consent/HIPAA/ Medical Release Form	x						x
Master Enrollment Log	x						
Inclusion/Exclusion Checklist +	x						
Locator Form	x		x	x	x		x
Demographics	x						
Medical History	x						
Substance use history	x						
Charlson Comorbidity Index	x						
Concomitant Medications	x		x	x	x		x
Study Completion					x	x	
Protocol Deviations							x
Missed Visit							x
Safety Assessments							
Patient Health Questionnaire (PHQ-9)	x		x	x	x	x	
P4 suicide screener (P4 screener) (Follow-up assessment will be triggered by the PHQ-9 result) ++	x		see ++	see ++	see ++		x
Safety Event Response Checklist	x		x	x	x		x
Pregnancy and birth control assessment	x		x	x	x		x
Substance Use Assessments							
Urine Drug Screen (UDS) (the OTP records)	x		x	x	x		x
Timeline Followback (TLFB)	x		x	x	x	x	
Methadone Treatment and Satisfaction Assessments							
Methadone Call Back (once)			see +++	see +++	see +++		x+++

Study visit number	Visit 1	Visit 2*_	Visit 3	Visit 4	Visit 5	Early termination	
Visit location**	OTP/remote	Pharmacy	OTP, Pharmacy, remote	OTP, Pharmacy, remote	OTP, Pharmacy, remote	OTP, Pharmacy, remote	
Assessment/Activity	Screening/Baseline	Methadone dosing and dispensing	1 Month After Visit 2	2 Months After Visit 2	3 Months After Visit 2		As needed
(the OTP records)+++							
OTP's Psychosocial Counseling Attendance Form (the OTP records)	x		x	x	x	x	
Methadone Visit Checklist++++		x	x	x	x		x
End of Methadone Medication Form					x	x	
Treatment Satisfaction Survey	x		x	x	x	x	

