Hospitalizations: Hospitalization for any medical and/or psychiatric reason will be reported accordingly on the Safety Event Response Checklist. All hospitalizations will be assessed by self-report at each monthly research visit or Early Termination Visit if participant discontinues study participation early.

Overdoses: Non-fatal overdoses since the last visit will be captured via self-report using the Safety Event Response Checklist at each monthly research visit following consent. Research staff will report overdose events to PI who will arrange with the site PI to terminate the participant from the study and return the participant to the OTP for medication administration, change in take home regimen, and other appropriate

intervention. Data on fatal overdoses may be collected via medical chart record review, if medical records data is available, or during participant tracking for follow-up interviews. Information from records will be supplemented with information from contacts with persons listed on the participant's locator form when participants are lost to follow-up throughout the study. Fatal overdoses will be captured on the Safety Event Response Checklist.

Death: All deaths, regardless of cause, will be captured for this study. These events will be identified through the participants' locator information, or when possible through using state medical examiner records, National Death Index, and/or review of medical records. Deaths will be reported using the Safety Event Response Checklist.

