4.4.4. Methadone Treatment Assessments

Methadone Visit Checklist: This form will be completed by the study pharmacists to document all study medication administered and dispensed at each Pharmacy visit, including the daily prescribed dose of methadone and the lot number and expiration date of administered/dispensed medication. This form also will be used to document pharmacist-provided care, such as (1) performing methadone prescription reconciliation, (2) providing patient education (e.g., safe storage, medication side effects); (3) checking and recording the patient's controlled medications prescription status using the NC Controlled Substances Reporting System [CSRS]; (4) monitoring and recording safety related events/concerns and communicating with the OTP medical physician or staff promptly regarding the event/concern; and (5) administering one methadone dose at the pharmacy and dispensing methadone according to the prescription of the OTP physician and applicable federal/state guideline for methadone treatment for opioid use disorder. Communications between the study pharmacist and the OTP medical physician or staff will be documented on the form, such as reasons for changes in methadone doses and/or take-home schedule.

Methadone Call-Back: The OTP medical staff (e.g., nurse) will implement the call back procedure. This form will collect the written results provided from the OTP medical staff to document the outcome of each random methadone call-back visit during the study period (i.e., at least once for every study participant after the first methadone dispensing by study pharmacist(s)), including the amount of used and unused medication returned. Failure to successfully complete call back result in termination from the study and return of the participant to the OTP for further assessment and ongoing treatment. This Methadone Call-Back form will include questions assessing whether a random methadone call-back visit is completed, its date, and the outcome of the call back (e.g., brought back all doses or not). The OTP staff is required to sign and date the form that a call back was done and its results (e.g., brought back all doses or not).

Treatment Satisfaction Survey: Participants, pharmacists and methadone treatment physicians will be asked to rate their overall satisfaction with the quality of the treatment (modified from Harland et al., 2015). Participant

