13.2. Secondary Outcome Measures

- **Rate of recruitment of participants into trial:** The recruitment rate will be assessed on a monthly basis until the enrollment target is reached. The recruitment rate is operationalized as the total number of participants consented in one month. The per-month proportion of consented participants reaching the pharmacy follow-up phase will also be calculated, as well as the per-month proportion of pre-screened participants that were consented. These rates will be used to estimate the speed at which a future multi-site RCT could consent, enroll, and randomize participants.
- **Treatment retention in follow-up assessments:** Retention in follow-up assessments is defined as the proportion of study assessments completed (three follow-up assessments).
- **Opioid and other substance use:** The prevalence and frequency of opioid/heroin use and other substance use over the study duration will be examined.
- **Satisfaction of participants, physicians, and pharmacists with OUD care**

Satisfaction with treatment delivery by participants will be measured using the Treatment Satisfaction Survey (adapted from Harland et al., 2005) at each visit. The proportion of visits in which participants are satisfied (score of 4 on a Likert Scale of 1-5) or very satisfied (score of 5 on a Likert Scale of 1-5) will be calculated. Pharmacist and physician satisfaction with treatment delivery will be measured using the Treatment Satisfaction Survey on a monthly basis, and a proportion of physician and pharmacist monthly ratings of satisfied or very satisfied will be calculated.

- **Participant safety, as measured by:**

- a) Any fatal or non-fatal substance use-related overdose measured by self-report.
- b) Any substance use-related ED visit or hospitalization measured by self-report.

13.3. Statistical plan and data analysis.

This is a feasibility study, and as such there are no a priori hypotheses. The main objective is to understand the feasibility regarding the study design features and operational procedures in order to inform the design of a full scale clinical trial (e.g., whether participants can be recruited in a timely fashion, whether the collaboration between the OTP and pharmacist can ensure standard methadone treatment for Opioid Use Disorder).

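### ED visits, hospitalizations and non-fatal overdoses are measured by self-report only, and an event documented elsewhere in the study has no stated route into the safety outcome

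*Combined protocol and SAP*

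**What the plan says.** Section 13.2 lists participant safety as a secondary outcome with two parts. Part (b) is "Any substance use-related ED visit or hospitalization measured by self-report". Part (a) is "Any fatal or non-fatal substance use-related overdose measured by self-report". Objective h in section 2 also uses self-report for ED visits and hospitalizations. For overdose it reads "Any fatal or non-fatal substance-related overdose measured by medical examiner record or self-report, respectively", which makes self-report the measure of the non-fatal ones.

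Section 4.4.2 agrees: "All hospitalizations will be assessed by self-report at each monthly research visit or Early Termination Visit if participant discontinues study participation early". Non-fatal overdoses are likewise taken from the participant's own account on the Safety Event Response Checklist. Section 15.2 adds baseline and the Early Termination Visit for overdose, and Table 1 also marks the checklist for use as needed. Chart review, locator contacts, medical examiner records and the death index are named only for fatal overdose and death.

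On consequences, section 4.4.2 says that staff report overdose events to the PI. The two PIs then act together, and the stated action is: "terminate the participant from the study and return the participant to the OTP for medication administration, change in take home regimen". Section 15.2 repeats this. For other safety events, section 4.4.2 says only that extra OTP visits, or termination with a return to the OTP, may be needed.

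Two other information streams run alongside. In section 4.4.4 the pharmacist's Methadone Visit Checklist covers "monitoring and recording safety related events/concerns and communicating with the OTP medical physician or staff promptly regarding the event/concern". OTP records are abstracted for urine drug screens, call-backs and counseling attendance (Table 1, section 4.4.3). Table 1 also lists, at Visit 1, an "Informed Consent/HIPAA/ Medical Release Form".

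**The concern.** Self-report is the only source named for these outcomes, and the plan attaches a consequence to one of the answers. A participant who values pharmacy pick-up and take-home doses has a reason not to mention an overdose. For other safety events the reason is weaker, because the consequence is conditional.

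If the pharmacist or the OTP learns of an event that the participant does not report to research staff, section 13.2 gives no way to count it. Section 15.2 nevertheless sets out to collect all ED visits, hospitalizations, overdoses and deaths among consented participants. The omission works in one direction: it can remove cases and cannot add them. The result would go forward to the planned randomized trial, where a report of no events would be read as reassurance about pharmacy dispensing.

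**Working it through.** The plan gives no event rate, power or precision figure for this outcome, so there is none to reproduce. The check has a textual part and an arithmetic part.

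**Text: source named for each event**

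| Event | Source named | Where |
|---|---|---|
| ED visit, hospitalization | Self-report | Objective h(2); 4.4.2; 13.2(b) |
| Non-fatal overdose | Self-report | Objective h(1); 4.4.2; 13.2(a); 15.2 |
| Fatal overdose | Self-report in 13.2(a); examiner record in objective h(1); records and locator contacts in 4.4.2 and 15.2 | As listed |
| Death | Locator information, examiner records, death index, medical records | 4.4.2; 15.2 |

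The first two rows have one source throughout. No section says how to treat such an event when it is documented elsewhere but not self-reported. The conflict in the fatal-overdose row is a separate matter that also needs reconciling.

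**Arithmetic: weight of one case**

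Input: n = 20, the maximum in section 4.1. Limits are exact (Clopper-Pearson), two-sided 95%.

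- 1/20 = 5%. Lower limit = 1 − 0.975^(1/20) = 0.13%. Upper limit = 24.9%.
- 0/20 = 0%. Upper limit = 1 − 0.025^(1/20) = 16.8%.

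**Illustration: incomplete self-report**

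Let s be the fraction of affected participants who self-report. The documents give no value, so 1.0 to 0.4 is an assumed range. Recorded risk = true risk × s. After 0/20 recorded, the upper limit on true risk is 16.8%/s. At an assumed true risk of 10%, the chance of recording at least one case is 1 − (1 − 0.10 × s)^20.

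| s (assumed) | Upper limit on true risk after 0/20 | Chance of at least one recorded case at 10% risk |
|---|---|---|
| 1.0 | 16.8% | 87.8% |
| 0.8 | 21.1% | 81.1% |
| 0.6 | 28.1% | 71.0% |
| 0.4 | 42.1% | 55.8% |

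**Illustration: adding a second source**

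Suppose a second source captures a fraction s2 of cases independently of self-report. Combined capture = 1 − (1 − s)(1 − s2). With s = 0.6 and s2 = 0.5 to 0.8 (both assumed), this is 1 − 0.4 × 0.5 = 0.80 to 1 − 0.4 × 0.2 = 0.92, and the limit falls from 28.1% to between 21.1% and 18.3%. If the second source holds only cases that the participant also reports, nothing is gained and the limit stays at 28.1%. The real benefit lies somewhere in that span.

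**The case against.** The best defence has five parts.

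- **No rule discards events.** Sections 4.4.2 and 15.2 speak of collecting all such events, and section 15.3 requires protocol-defined safety events to be assessed, documented and reported. The reporting process is left to the Manual of Operating Procedures, which is not in the documents and might already handle several sources. This stands as far as it goes. But these are collection and reporting statements, whereas section 13.2 states how the outcome is measured, and there the only source is self-report.
- **The stated consequence does not cover everything.** A reader might infer that any disclosure ends participation. The documents state that for overdose events. For other safety events termination is only possible.
- **The other sources are unproven.** A reader might infer that the study already holds hospital or ED data. Nothing shows that the OTP records contain them, and the scope of the medical release is not visible. The pharmacist may depend on what the participant says, so the same reluctance could apply. This stands, and it limits the expected gain.
- **Capture is not confined to monthly visits.** It also occurs at early termination and as needed, as well as at baseline. Over about 3 months, pharmacy pick-ups after day 0 number about 6 (every two weeks: days 14 to 84) to 12 (weekly: days 7 to 84), against three interviews. Since the overdose question covers the whole interval since the last visit, more contacts do not by themselves mean better capture.
- **The stakes are modest.** The outcome is secondary, descriptive and free of hypotheses, in at most 20 stable patients without a comparator. The intervals for 1/20 and 0/20 overlap heavily. This is why the point is a sensible correction and not a threat to the study.

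**Conclusion.** The point holds in limited form. Self-report is the sole named measure of ED visits, hospitalizations and non-fatal overdoses. An event documented by the pharmacist or the OTP but not self-reported has no stated route into section 13.2, which sits badly with the aim of collecting all such events. Omitting such cases can only bias the count downward.

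Each omitted case is worth 5 percentage points at n = 20. One of them moves the result from 1/20 (0.1% to 24.9%) to 0/20 (upper limit 16.8%). The larger upper limits, such as 28.1% at 60% capture, rest on assumed capture fractions and show sensitivity only.

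It would go too far to conclude that under-reporting will occur, or that contradictory data will sit on the study's forms. The documents give neither an under-reporting rate nor the number of events that the other sources would hold. The termination and take-home rules themselves are not judged here. They matter only because they can influence what participants report.

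**What to change.** In section 13.2(b), the non-fatal part of 13.2(a), objective h and section 4.4.2, with matching wording in 15.2:

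- Count a participant as having the event if it is documented by self-report, on the Methadone Visit Checklist, or in the OTP records already abstracted.
- Record the source or sources on the Safety Event Response Checklist.
- Report the self-report-only count beside the any-source count, so that the measure now planned stays visible and any gap can inform the later trial.
- Use records under the medical release only where they are already obtained. Requesting them from outside facilities would be an extra procedure and is not part of this change.
- If the Manual of Operating Procedures already has a multi-source rule, carry it into section 13.2.

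Because the outcome is whether a participant had any event, one event found in two sources is not counted twice.

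The cost is a change of outcome wording, one source field, and a brief addition to the OTP record abstraction; no new visits are needed. The downsides are that the reported rate may look less favourable and that the second sources may be incomplete, so the any-source count is still a minimum.
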